## 2 TRIALS METHODS

### 2.1 Trial design

DIVE-1 is a proof of concept study with three phases:

- a first safety phase (phase I) with administration of intracerebroventricular dopamine (intervention) according to a very careful slow titration protocol.
- a second efficacy phase II study (including patients enrolled in phase I who reached the titration objective without complications) using a randomized 2x2 cross-over design with administration of intracerebroventricular dopamine as intervention condition and usual optimized oral medical treatment alone as control condition
- a long-term follow-up phase of ICV dopamine administration restricted to patients enrolled in phase II study.

Each study phase is fully detailed in study protocol, according to study flow provided in figure 1.

Briefly, in first safety phase I, a slow titration of intracerebroventricular dopamine administration including one to one (namely, the second patient will be included after the end of titration period of the first patient, and so on) and with an independent Monitoring Committee who will review all adverse events.

The following go no go safety rule is applied to go to phase II:

- 1) for the first 5 patients, if no or at most one serious and unexpected adverse events (apart from the rare surgical risks of haemorrhage and infection with no impact in vital and functional prognosis of the patient) is observed, 15 other patients may be included and phase II will be start.
- 2) If two or more serious or unexpected adverse events (apart from the rare surgical risks of haemorrhage and infection with no impact in vital and functional prognosis of the patient) occur in first five patients, only 5 new patients could be included, and the following rule will be proposed to the independent Monitoring Committee:
  - if no or at most one of serious and unexpected adverse events among the 5 new patients, 10 other patients will be included in phase I and phase II can be started

[figure not shown]
- if two or more serious or unexpected adverse events among the 5 new patients, the Independent Monitoring Committee could decide to stop the study.

During phase I, Independent Monitoring Committee will be aware for each unexpected adverse events one patient at a time up and can propose to stop the study at any time.

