***Primary outcome:***

A case-report descriptive analysis will be done by reporting individual values of primary outcome according to the two periods as well as by using spaghetti plots showing the individual change from control to experimental period (by indicating the sequence of treatment). We also reported the mean, median and range values for control and experimental period. To assess the treatment effect (experimental vs. standard treatment) on primary outcome, we will use a Wilcoxon 'signed rank test. We will also report the standardized differences (Hedges'g) calculated from the within-patient's differences (E1-S2 and E2-S1) as effect size (calculated on rank transformed data).

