### 5.2.3 Long term follow-up

***Primary outcome:***

The percentage in "on" time without dyskinesia and with or without slight bradykinesia during a 7 day consecutive period (assessed using patient diary) between the last available follow-up and the evaluation during the treatment period of phase II part of DIVE will be done using a linear mixed model including phase (phase II vs. long term follow-up), and delay from phase II evaluation to long-term follow-up evaluation as fixed effects and patients as random effects to account the within intra-patients correlation. In cases of deviation to normality of model residuals, the difference between the phase II evaluation to long-term follow-up evaluation between the two evaluations by using a Wilcoxon-rank signed test.

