***Secondary outcomes:***

The same methods described to analyse the primary outcome of long-term follow-up phase will be used to analyse secondary and exploratory quantitative outcomes.

The frequency of adverse events from end of phase II trial to the last available follow-up will be reported.

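### The long-term switch to the signed-rank test is judged on mixed-model residuals instead of the within-patient changes, which can hide skewed changes if the two evaluations are highly correlated

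*SAP*

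**What the plan says.** SAP section 5.2.3 analyses the long-term primary outcome (a diary percentage) with a mixed model that has fixed effects for phase and for delay and takes "patients as random effects to account the within intra-patients correlation". Two values enter per patient: the one from phase II treatment and the last available follow-up. The move to a signed-rank test is conditional, in a sentence that opens: "In cases of deviation to normality of model residuals, the difference between the phase II evaluation to long-term follow-up evaluation". No normality test, threshold or type of residual is named.

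The rule reaches further than one outcome: "The same methods described to analyse the primary outcome of long-term follow-up phase will be used to analyse secondary and exploratory quantitative outcomes". Section 5.5 plans no sensitivity analysis, so nothing stands behind whichever branch is taken.

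Phase II is handled differently. Section 5.2.2 has no switch and names the signed-rank test outright: "To assess the treatment effect (experimental vs. standard treatment) on primary outcome, we will use a Wilcoxon". The revision history gives the small sample (9 analysable patients against 20 planned) as the reason. The long-term phase is "a long-term follow-up phase of ICV dopamine administration restricted to patients enrolled in phase II study", so it gains no new patients, yet it keeps the route that starts from the parametric model.

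**The concern.** The mixed-model phase test and the signed-rank fallback both rest on the within-patient change. A check that decides between them should look at the distribution of that change. Residuals from a random-intercept model with two rows per patient do not show it faithfully: a patient with one very large change contributes one large negative and one large positive residual, and the set looks more symmetric than the changes are.

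The pattern at risk is a small loss in most patients and a large loss in one or two. The large losses inflate the standard error of the phase term, the residual check may pass, and the analysis stays with the model when the signed-rank test would have been the stronger choice.

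**Working it through.** **Inputs.** From the SAP: two-sided 5% level (3.1); SD 15 and correlation 0.5, stated for PTO in phase II only (2.3); 9 patients with complete phase II primary data and a production cap of 12 patients (2.3); long-term set defined by at least 6 months of further treatment (3.3). Assumed, because the SAP is silent: n = 9 or 12; correlation 0.5, 0.8 or 0.9; Shapiro-Wilk at 5% as the check; conditional residuals; delay constant within patient.

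**The plan's own figure.** The only power statement is for phase II. SD of the difference = 15 × √(2 × (1 − 0.5)) = 15. A paired t test of a 10-point difference with 20 patients has power 0.807, which agrees with the stated value above 80%. There is no corresponding figure for the long-term test.

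**Residuals.** Let m be the centred patient mean, d the centred change and k the shrinkage factor. A patient's two residuals are (1 − k)m + d/2 and (1 − k)m − d/2. With a = (1 − k)m and b = d/2, their cubes sum to 2a³ + 6ab²; the b³ term, which carries the skewness of the changes, drops out. With true variances k = 2ρ/(1 + ρ), so 1 − k = (1 − ρ)/(1 + ρ), which is 0.33 at ρ = 0.5, 0.11 at 0.8 and 0.05 at 0.9. An extra loss L moves m by −L/2 and d by −L. Before centring, the follow-up and phase II residuals move by:
- ρ = 0.5: −0.67L and +0.33L
- ρ = 0.8: −0.56L and +0.44L
- ρ = 0.9: −0.53L and +0.47L

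The higher the correlation, the closer the two are to mirror images. (k is estimated in practice, and large losses pull it down somewhat.) In one simulated data set with ρ = 0.8 the skewness was −1.00 for the changes and −0.44 for the residuals; Shapiro-Wilk p was 0.042 and 0.56.

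**Simulation, n = 9, SD 15, 2,000 runs per setting.** Every patient has the common loss; one or two have the extra loss as well.

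| ρ | Common loss | Extra loss | Check fires: residuals / changes | Detection: as written / changes checked |
|---|---|---|---|---|
| 0.5 | 10 | 40 in one | 13% / 15% | 51.8% / 52.4% |
| 0.5 | 10 | 40 in two | 10% / 10% | 62.9% / 63.8% |
| 0.8 | 10 | 40 in one | 20% / 42% | 74.2% / 79.8% |
| 0.8 | 10 | 40 in two | 11% / 34% | 84.7% / 86.6% |
| 0.8 | 10 | 60 in one | 55% / 84% | 70.1% / 77.7% |
| 0.8 | 10 | 60 in two | 37% / 78% | 80.1% / 85.9% |
| 0.9 | 5 | 40 in one | 33% / 79% | 37.2% / 51.3% |
| 0.9 | 5 | 40 in two | 13% / 70% | 49.2% / 63.0% |

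The differences are 0.6 to 0.9 points at ρ = 0.5, 1.9 to 7.6 at 0.8, and 13.8 to 14.1 in the two settings at 0.9.

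**n = 12, extra loss 40 in one or two.** At ρ = 0.8 and common loss 5, detection goes from 41.2% to 44.4% and from 54.4% to 56.2%; with common loss 10, from 92.2% to 93.4% and from 94.8% to 95.2%. At ρ = 0.9 and common loss 5 it is larger: 62.9% to 68.4% and 68.0% to 75.6%.

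**No common loss, 60 points in two of 9.** Detection as written and with the changes checked is 7.4% and 8.2% (ρ = 0.5), 4.2% and 7.0% (0.8), 4.0% and 8.0% (0.9). The signed-rank test alone does no better than about 10%.

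**Level, and the cost of signed-rank throughout.** With normal changes and no loss, either rule rejects in about 5% of runs. The exact signed-rank test at n = 9 attains 2 × 10/512 = 3.9%. With normal changes and a common loss of 10 its power is 26.0% against 33.6% for the model at ρ = 0.3, and 94.9% against 97.0% at ρ = 0.9.

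**The case against.** Checking mixed-model residuals is conventional, and the only correlation in the SAP is 0.5. At that value the residual check fires about as often as a check of the changes, and the model is mostly no weaker than the signed-rank test (for example 0.63 against 0.55 with two extra losses of 40). Large effects need a high correlation: a phase II SD of 15 with an independent change SD of 5 or 6 gives a gain of 11 to 15 points, but implies a correlation of 15/√250 = 0.95 or 15/√261 = 0.93 before the extra losses. Nothing in the SAP supports such values. This stands, and it limits the size of the point. It does not settle it, because the 0.5 was given for PTO and not for a diary outcome.

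A reader might draw three stronger conclusions that the SAP does not support:
- That the trigger explains why a loss in only one or two patients is missed. It does not; no option detects such a loss at these sample sizes.
- That the check usually fails to fire. With a 60-point loss in one of 9 patients at ρ = 0.8 it fires in 55% of runs.
- That the long-term set cannot exceed 9. That figure counts patients with complete phase II primary-outcome data, whereas long-term patients are defined by enrolment in phase II and duration of treatment, and the production cap is 12.

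Reading a non-significant loss as maintenance is a separate problem, which a different trigger does not cure.

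**Conclusion.** The point holds in a limited form. The trigger looks at a quantity other than the one being tested, and this follows from the model whatever the data. Its practical cost is conditional. With about 9 patients, a correlation of about 0.8 to 0.9, a small loss in most patients and a large loss in one or two, detection falls by about 4 to 13 points (individual settings run from 2 to 14). At 12 patients it falls mostly by 1 to 3 points, and by up to about 8 at a correlation of 0.9. At 0.5 it is about 0 to 1 point. These figures assume Shapiro-Wilk at 5%, conditional residuals and delay constant within patient. Checking the changes kept the 5% level and was within simulation error of the current rule or better, so the improvement is worth making although its size is uncertain.

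**What to change.** In SAP section 5.2.3, replace the condition "In cases of deviation to normality of model residuals" by non-normality of the within-patient changes (last follow-up minus phase II), and name the check and its threshold. State that the same trigger governs the long-term secondary and exploratory quantitative outcomes. This takes a sentence or two and no new data, and costs essentially nothing when the changes are normal.

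Using the signed-rank test throughout, as section 5.2.2 does for phase II, is an option that removes the switch altogether. It is a trade-off, because it loses some power when the changes are normal or the evaluations only moderately correlated.

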***Secondary outcomes:***

The same methods described to analyse the primary outcome of long-term follow-up phase will be used to analyse secondary and exploratory quantitative outcomes.

The frequency of adverse events from end of phase II trial to the last available follow-up will be reported.

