***Long term follow-up study:***

The primary objective is to assess the maintenance of efficacy of long-term continuous administration of intracerebroventricular dopamine on motor control and non-motor complications.

Secondary objectives are

- 1) To assess the maintenance of efficacy on:

- motor aspects
- cognitive-behavioural aspects: drowsiness, anxiety, depression, apathy, sleep, hallucinations
- cognition and psychiatric assessment
- quality of life
- general condition

- 2) To assess the maintenance of tolerance of intracerebroventricular dopamine administration

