#### **2.4 Framework**

Primary and secondary comparative objectives of phase II part of DIVE-1 trial are tested for superiority in favour of intervention versus control treatment period. For phase I study, none statistical tests will be done and only descriptive analysis with go no go rule for safety will be done. For long term follow-up phase, intra-patient comparisons will be done to assess the maintenance efficacy and safety.

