#### **3.3 Analysis population**

For phase I study, all included patients who have been operated, whatever they received or not a dose of study treatment, will be considered in analysis as a safety population.

For the phase II study, regarding the proof of concept, the efficacy population will include all randomized patients, who completed the two-treatment period with available primary endpoint —and without major protocol deviation. All patients randomized and excluded from the efficacy population will be described with the reason of exclusion. The safety population of phase II study will include all randomized patients who receive ICV dopamine (or placebo).

For the long-term phase part of study, all patients having received ICV dopamine for at least 6 months after end of the phase II part will included in the analysis population of long-term phase part of DIVE-1 study.

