***Secondary outcomes of safety:***

- MDS-UPDRS parts I
- Epworth Sleepiness Scale and Parkinson's Disease Sleep Scale
- Cognitive measures (MOCA, NPI, PAS, LARS and ECMP)
- Psychiatric tolerance: a score from a simple questioning on the disorders (no thymic, anxious, psychotic decompensation).
- Frequency of adverse events during the 4 weeks of treatment period reported by the patient and/or noted by the investigator according to clinical examination, ECG, blood pressure, pulse and biological assessment (standard biology, biological iron assessment, blood and urinary levels of dopamine and its metabolites (HVA and 5-cysteinyl-dopamine) and variations in weight, temperature, and blood pressure on the orthostatic hypotension test.

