***Secondary outcomes:***

For secondary and exploratory quantitative outcomes, only a descriptive analysis will be done by reporting the mean, median and range values as well as plotting the values using spaghetti plots showing the change from control to experimental period (by indicated the sequence of treatment using dedicated colors). We will also report the standardized differences (Hedges'g) calculated from the within-patient's differences (E1-S2 and E2-S1) as effect size (calculated on rank transformed data). The frequency of adverse events during the 4 weeks of treatment period will be reported in each treatment group without statistical comparison.

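### Long-term adverse events are summarised as a raw frequency over an open, unequal follow-up with no exposure denominator, and the SAP gives two conflicting windows for them

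*SAP*

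**What the plan says.** Five places in the SAP bear on this point.

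- **Section 1.3, long-term objectives.** One secondary objective is: "To assess the maintenance of tolerance of intracerebroventricular dopamine administration".
- **Section 2.4, Framework.** For the long-term phase, "intra-patient comparisons will be done to assess the maintenance efficacy and safety".
- **Section 3.3, Analysis population.** The long-term population is "all patients having received ICV dopamine for at least 6 months after end of the phase II part".
- **Section 5.2.3, Secondary outcomes.** The only adverse-event analysis for this phase is: "The frequency of adverse events from end of phase II trial to the last available follow-up will be reported". The phase II counterpart, in section 5.2.2, is: "The frequency of adverse events during the 4 weeks of treatment period will be reported in each treatment group without statistical comparison".
- **Section 5.1.3, Secondary outcomes of safety.** The long-term adverse-event outcome is defined as: "Frequency of adverse events during the 4 weeks of treatment period reported by the patient and/or noted by the investigator". The same list contains MDS-UPDRS part I, sleep scales, cognitive and behavioural measures and a psychiatric tolerance score.

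The model in section 5.2.3 includes the delay since the phase II evaluation, but it is extended only to quantitative outcomes. Sections 5.5 and 5.6 plan no sensitivity or additional analyses.

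**The concern.** Maintenance is a statement relative to an earlier state. A reader of the final report will look at the long-term adverse-event frequency and ask whether it is better or worse than what was seen on ICV dopamine in phase II. As written, the two figures cover very different lengths of time, and nothing in the SAP scales either by exposure. An unchanged event rate would look like worsening tolerance, and even an improved rate could look that way.

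The long-term figure is also hard to read by itself. Follow-up runs to each patient's final available assessment, with no common cut-off, so patients followed longer contribute more events for that reason alone.

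The window is not settled either. The definition in section 5.1.3 and the analysis in section 5.2.3 cannot both apply, so the statistician has no single outcome to program.

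**Working it through.** **No figure to reproduce.** The SAP states no adverse-event rate and no expected length of long-term follow-up. The 4-week risks below are assumptions, shown over a range.

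**Inputs from the SAP**
- Phase II window: 4 weeks per treatment period (section 5.2.2).
- Long-term window: end of phase II to last follow-up (section 5.2.3), with at least 6 months on ICV dopamine (section 3.3), taken as 26 weeks.
- Numbers: at most 12 patients, 9 with complete primary data (section 2.3). The number entering the long-term phase is not stated.

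**Step 1: ratio of windows.** 26/4 = 6.5, and 52/4 = 13 at one year. With a constant rate, expected events per patient rise by these factors.

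**Step 2: patients with at least one event.** If p is the 4-week risk and the hazard is constant, the risk by week w is 1 − (1 − p)^(w/4).

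| Assumed 4-week risk | By 26 weeks | By 52 weeks |
|---|---|---|
| 5% | 28% | 49% |
| 10% | 50% | 75% |
| 20% | 77% | 95% |
| 30% | 90% | 99% |

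For p = 20%: 1 − 0.8^6.5 = 0.766. For p = 10%: 1 − 0.9^6.5 = 0.496. Relative to the 4-week figure these are 3.8-fold and 5.0-fold increases at 26 weeks, with no change in tolerance.

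**Step 3: could an improvement be hidden?** Halve the hazard after phase II. A 4-week risk of 20% still gives 1 − 0.8^(6.5/2) = 52% at 26 weeks. For the raw event count not to rise, the recorded rate would have to fall to 4/26 = 15% of the phase II rate at 26 weeks, or 4/52 = 8% at 52 weeks.

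**Step 4: what a patient-time rate does.** With p = 20%, the rate is −ln(0.8) = 0.223 events per patient per 4 weeks. A month is 52/12 = 4.33 weeks, so this is 0.223 × 4.33/4 = 0.24 per patient-month. At a constant hazard it is the same in both phases, and the artefact disappears.

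**Step 5: precision.** Nine patients over 4 weeks give 36 patient-weeks, or 36/4.33 = 8.3 patient-months. At p = 20% about 9 × 0.223 = 2.0 events are expected in the phase II ICV dopamine periods; with 12 patients, 12 × 0.223 = 2.7. The phase II side limits any comparison.

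**Step 6: the two windows side by side.** Section 5.1.3 counts events in a 4-week treatment period; section 5.2.3 counts them over the whole of long-term follow-up. The long-term phase as described has no 4-week treatment period. The definition nearly repeats the phase II entry in section 5.1.2, so it may have been carried over, but the SAP does not say so.

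**The case against.** The strongest reply is that section 5.2.3 merely promises to report a frequency. It names no phase II comparator, and section 5.2.2 excludes statistical comparison for phase II adverse events. The within-patient comparison promised in section 2.4 is worked out for the quantitative outcomes, and section 5.1.3 lists several scales that bear on tolerance. This stands. A reader might infer that maintenance of tolerance will be judged by setting the raw long-term frequency against the phase II frequency; the SAP does not say that, and adverse events are only one component of the objective. The point survives in narrower form: without exposure, the adverse-event component cannot inform the objective, whether or not a formal comparison is made.

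A reader might also infer that wider visit spacing adds to the rise. The direction is wrong. Table 1 puts long-term visits every 6 months, and sparser visits would tend to lower the recording of mild events. Nor can one conclude that contact falls to once in 26 weeks: section 1.1 describes regular pump filling and section 3.2 refers to checks before each refill. Differing capture is a caveat, acting against the exposure effect by an unknown amount.

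It is also fair that the percentages rest on assumed risks, that the SAP does not say whether frequency means patients or events, and that the exposure mismatch would vanish if the 4-week definition in section 5.1.3 governed. The first affects the size and not the direction; cumulative patients and cumulative events both grow with time. The last is a reason to settle the window first.

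**Conclusion.** The point holds for the adverse-event component of the long-term tolerance objective. Under section 5.2.3 the summary grows with follow-up by construction, and it cannot be read against the 4-week phase II figures or between patients with different follow-up. At an unchanged hazard, assumed 4-week risks of 5% to 30% become 28% to 90% by 26 weeks; expected event counts rise 6.5-fold. These sizes assume a constant hazard, equal capture in both phases and 6 months taken as 26 weeks. If long-term capture is lower, the recorded rise would be smaller.

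Separately, and without any assumption, sections 5.1.3 and 5.2.3 give incompatible windows for one outcome.

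The finding does not show that the SAP plans an invalid test, or that overall tolerance will be misjudged, since other safety measures are analysed with time in the model.

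**What to change.** 1. Reconcile the adverse-event window in sections 5.1.3 and 5.2.3 so that one definition applies, and say whether patients, events or both are counted.
2. In section 5.2.3, report adverse events as events per patient-month of ICV dopamine, with patient-months shown, for the phase II ICV dopamine period and for the long-term phase.
3. Add a caveat that capture may differ between phases because visit schedules differ, which would tend to lower recorded non-serious events in the long term.

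The cost is a few lines of SAP text and a denominator computed from dates already collected. The downside is that a rate assumes a roughly constant hazard over the interval it covers and will be imprecise with about 9 to 12 patients, so it should be presented descriptively. Confining the comparison to serious events, or to those leading to stopping or hospital contact, would reduce dependence on visit frequency but discard much of the tolerance information; that trade-off is debatable and is not part of this recommendation.
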